1. Open name of research :Effect of dual task balance training on cognitive functions in people with mental retarded.

2. Open name of the researcher / researchers:

2.2.5. Faks numarası:-

2.2.6. E-mail: [contact]

3. Purpose of the study:

With this study, it will be tried to determine whether the addition of physiotherapy program to the education of mentally disabled individuals is effective and necessary in terms of mental performance.

4. MATERIÉLS AND METHOTS

Mental disability levels IQ = 50-79 individuals with mild / border mental disabilities will be included in the study. The disability status of the individuals will be determined by the health report, and the cognitive status of the individuals will be determined by the report given as a result of the evaluation made by the Guidance Research Centers of the National Education Directorates. The 45-person study group will be randomized to 3 groups of 15 persons each. The first group will not be subjected to any application except education. The second group will be the control group and will be taken to the balance training in addition to normal education. In the third group, dual task balance training will be applied within the scope of cognitive rehabilitation. The study will be held from December 2018 to December 2019. Intelligence-related parts of the assessments will be carried out by the expert psychologist. The studies were planned to be 2 times a week for 12 weeks. Before the beginning of the study, at the end and 3 months after the end of the study, the assessments for the groups will be applied and the results will be evaluated statistically within and between the groups. Inclusion

criteria; IQ 50-79, 6-13 years old, take command of Turkish, do not have physical disability, not have metabolic and systemic disease. To have a report on the mental disability and education required by the Ministry of National Education.

Exclusion criteria; To have any situation that prevents the taking of commands related to the exercise program to be implemented, To have a chronic systemic disease, To have an educational diagnosis other than the mental disability.

MOXO Attention Test: Attention, Timing, Impulsivity and Hyperactivity were found to be very effective in measuring performance levels; however, the rapidly increasing popularity of the test is due to the unique Distractor System found in MOXO.

To be able to focus on a simple MOXO task, the individual must ignore the visual and auditory distractors in the test, just as they should do in the same daily life. Individual; In order to achieve this, they must ensure the active inhibition of distractors, which makes the test even more challenging and the advanced characteristics of the test.

WISC-R INTELLIGENT TEST: It is a intelligence test prepared by David Wescler in 1939. This test, which first appeared for adults, was redesigned for children with the arrangements made. The WISC-R Child Intelligence Test is suitable for children aged 6 to 16 years. The individual test is 1-1,5 hours.

Wisc-r intelligence test is a test performed by an expert. WISC-R Intelligence Tests are divided into two main parts.

Verbal Intelligence Departments, Performance Intelligence

There are 6 tests in both sections. Tests for these two sections are given one after the other.

Bruininks-Oseretsky motor competence test: BOT-2 is a set of targeted activities to measure a wide range of motor skills in people aged 4 to 21 years. This test is a tool designed to provide an effective and reliable measurement of fine and rough motor control skills to physiotherapists, researchers and other practitioners. The Bruininks Oseretsky motor proficiency test (BOTMP; Bruininks), first published in 1978, was the most widely used standard measure (R. Bruininks and B. Bruininks, 2005 (3)). While the Bruininks Oseretsky motor competence test (BOT-2) designed to facilitate the evaluation lasts 40-60 minutes for all children with 53 items, the highest score is 320 for this test. The application of the short form of the test, which consists of 14 items, lasts 15-20 minutes the highest score is 88 (R. Bruininks and B. Bruininks, 2005).

COGNIBOARD: CogniBoard is a device that helps the healing process in patients with neurological or orthopedic injuries and diseases, provides multiple exercises, and develops and measures cognitive and motor performance in healthy individuals and athletes. CogniBoard consists of a 64-illuminated button placed on the panel that can be adjusted to the size of the individual. The layout of the keys creates a specially designed 5-ring. The individual is accompanied by lighted instructions and audible warnings are accompanied by exercise. Thus, tactile, visual, proprioceptive and auditory feedback is provided.

Functional Reach Test: The person is asked to lift his right arm about 90 degrees and to make a fist in his hand while he is standing at barefoot as a barefoot. The distance between the third metacarpal in

each case indicates the functional extension. Decreased ability to reach in the future indicates that the risk of falling is approximately 8.2, the average is 4'dur never reach and those who can extend is less than 15.2cm.

PEDIATRIC BALANCE SCALE: Pediatric balance scale is a balance scale which is designed to require minimal special material use which is rated between 0-4 points for each movement according to the measure of success, in which 14 basic movements are evaluated.

Dual Task Balance Training Programs: Dual Task A progressive balance training program will be held twice a week for 12 weeks. Balance training 10 min. start with warming. The first 5 minutes of warming is planned on walking on the treadmill, the next 5 min. The 20-minute Dual Task balance training program is planned to be composed of two sections of 10 minutes. In the first 10 min section, the individual will exercise with the multi-task mode of CogniBoard on the balance ball. In this mode, when a random light goes out, the second light is turned on and the individual presses the button and the process is turned on for 10 minutes. Will be asked to continue throughout. This mode aims at neurocognitive procedures such as attention, short-term memory, hand-eye coordination, focusing and perception. Stroop study will be performed on the balance ball in the second 10 minutes of the exercise. In this study, it is aimed to develop neurocognitive procedures such as focused attention, response inhibition, disruptive effect resistance, information processing speed.

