4.1. Number of volunteers::45

4.2. STATISTICS

In the analysis of the results to be obtained in our study, SPS statistics 22.0 version of SPSS statistics will be used under the Windows operating system Statistical Package for Social Sciences (SPSS). Descriptive statistical information shall be shown as arithmetic mean \pm Standard Deviation (\bar{x} istatistiksel \pm Ss) or percentage (%) and the statistical significance level shall be considered as $p \leq 0.05$.

The difference between the groups will be tested by two-factor variance analysis.

The two-factor variance analysis for correlated or repetitive measurements is an independent variable with two or more groups and associated or repeated measurements. Associated or repetitive measurements should be performed on the same subjects at specific time intervals. The purpose of this test is to determine the effect of the independent variable on the associated measurements. Specifically, it is to determine whether the groups of the independent variable have a different effect between the associated or repeated measures. TWO-WAY ANOVA

5. Center / centers where the research will be carried out: The research will be conducted between December 2018 and December 2019 in "Gerçek Dünya" special education and rehabilitation center and "Fark" special education and rehabilitation center.

6. Applicant's:

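### Ages 6-13 are randomised with no stated balancing on age and analysed with no age term; stratifying by age and adjusting change for it is a cheap improvement

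*Protocol*

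**What the plan says.** Protocol section 4 (materials and methods) sets the age range among the inclusion criteria: "criteria; IQ 50-79, 6-13 years old, take command of Turkish". Its only statement on allocation is "The 45-person study group will be randomized to 3 groups of 15 persons each". Section 4.1 repeats the total: "4.1. Number of volunteers::45". No stratification, matching or minimisation on age or any other factor is described.

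The same section describes the motor and balance measures in their own units. For the full BOT-2, "the highest score is 320 for this test"; the short form "lasts 15-20 minutes the highest score is 88". The functional reach test is a distance, with a threshold given in centimetres ("those who can extend is less than 15.2cm"). The Pediatric Balance Scale is one "which is rated between 0-4 points for each movement according to the measure of success, in which 14 basic movements are evaluated", so its implied maximum is 14 x 4 = 56. No age-standardised motor score is mentioned.

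Section 4.2 plans a two-factor analysis of variance, with group as one factor and repeated measurement as the other. Neither age nor any other covariate is named. Assessments are made before training, at its end and 3 months later.

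**The concern.** Children of 6 and 13 can be expected to differ in body size, motor skill, attention and capacity to do two tasks at once. Age is therefore likely to show in a point total or a reach distance, and it may also affect how much a child gains from 12 weeks of training. On a bounded scale, a child who starts near the top has little room to improve.

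With 15 children per group, chance alone can leave the groups visibly different in age. As written, the allocation, the description of the scores and the named analysis all leave age out. A reader of the results could then ask whether a difference in response reflects the training or the ages of the children, and the planned analysis would have no answer. Age is known for every child at entry, so the gap can be made much less likely. That has to be decided before the first child is allocated; a later analysis plan cannot change how the children were assigned.

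**Working it through.** **Inputs from the protocol.** Ages 6-13; 45 children; 3 groups of 15. The total is consistent (3 x 15 = 45, as in section 4.1). The protocol gives no effect size, SD or power, so there is no stated calculation to reproduce.

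**Assumed input.** The SD of age among enrolled children is not in the document. If ages are even from 6 to the 14th birthday, SD = 8/√12 = 2.31 years. If eligibility ends at the 13th birthday, SD = 7/√12 = 2.02. Normal distributions with SD 2.0, 1.5 and 1.0 show what happens as ages cluster.

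**Chance age gap without balancing.** For two groups of 15, SE of the difference in mean age = SD x √(2/15) = SD x 0.365. With SD 2.31 this is 0.84 year. For a given pair, P(gap > 1 year) = 2 x [1 − Φ(1/SE)] = 2 x [1 − Φ(1/0.843)] = 0.24. The chance that some pair among the three groups exceeds a limit was simulated (200,000 runs per row).

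| Assumed ages | SD | SE | Given pair > 1 y | Some pair > 1 y | Some pair > 1.5 y |
|---|---|---|---|---|---|
| Even, 6 to 14th birthday | 2.31 | 0.84 | 24% | 46% | 18% |
| Even, 6 to 13th birthday | 2.02 | 0.74 | 18% | 37% | 10% |
| Normal | 2.0 | 0.73 | 17% | 36% | 10% |
| Normal | 1.5 | 0.55 | 7% | 16% | 2% |
| Normal | 1.0 | 0.37 | 0.6% | 2% | under 0.1% |

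Re-randomising a fixed pool of 45 ages spread evenly over 6 to 14 gives much the same as the first row: 24% for a given pair and 48% for some pair.

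**With two age strata.** Each stratum is 4 years wide, so the SD within it is 4/√12 = 1.15 and the SE of a difference is 1.15 x 0.365 = 0.42 year. If every group holds 8 younger and 7 older children, some pair differs by more than 1 year in about 5% of randomisations. With permuted blocks of 3 applied to the evenly spread pool (23 younger, 22 older, so the last block in each stratum is incomplete), the figure is about 7%, and 3% for a given pair.

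**What a 1-year gap means for an outcome.** If an outcome or a gain correlates r with age, a 1-year gap shifts its mean by r x 1/2.31 SD: 0.13 SD at r = 0.3, 0.22 SD at r = 0.5 and 0.30 SD at r = 0.7. These correlations are assumptions. For scale, the difference that two groups of 15 detect with 80% power at two-sided 0.05 is (1.96 + 0.84) x √(2/15) = 1.02 SD. The protocol does not state sidedness.

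**Where the shift enters.** If age moves all three assessments by the same amount, it drops out of the group-by-time contrast. It stays if gain depends on age, if a bounded scale limits gain in children who start high, or if groups are compared at one time point.

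**The case against.** The strongest case against is that nothing here is wrong. Randomising 45 children without an age stratum is a valid design. Chance imbalance is not bias in expectation, and the type I error already allows for it. The group-by-time analysis also removes a constant age offset. All of this stands, and it limits the point to precision and credibility.

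Three stronger readings are tempting, and the protocol does not support them.

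- A reader might infer that simple, unrestricted randomisation was chosen. The protocol does not say so; exactly equal groups imply some restriction, and the method is left open.
- A reader might infer that raw, unadjusted scores will be analysed. The maxima and units come from descriptions of the instruments. Age-normed scores are not excluded, and an analysis plan that is not shown could use them or add age as a covariate.
- A reader might infer that an age gap would readily imitate or conceal a training effect. A shift of 0.13-0.30 SD is modest beside the roughly 1 SD that this trial can detect, and how far gain depends on age is not documented.

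The trial's stated purpose is mental performance, whereas the argument about units concerns only the motor and balance measures. The protocol does not say how the MOXO scores are scaled, so nothing is claimed there. The motor tests are still described among the study's measures, and section 4 plans comparisons of the assessments between groups.

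Age also competes with centre (two are named) and IQ as a balancing factor, and 45 children cannot support many strata. That is a fair reason to keep to two age strata. It is not a reason to leave age out, given how wide the range is.

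**Conclusion.** The point holds as a cheap improvement. The protocol states no balancing on age across a 6-13 range and no age term in the analysis. If ages fill the range (SD 2.0-2.3), a gap above 1 year between some pair of groups has a chance of about 36-46%. The figure rests on that assumed spread and falls to 16% at SD 1.5 and 2% at SD 1.0, so the point loses most of its force if the enrolled children are close in age.

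It would be wrong to conclude that the trial is biased or its planned test invalid. The harm is lost precision and a result that is harder to defend, confined to outcomes whose gain depends on age (ceiling effects included) and to comparisons at a single time point.

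**What to change.** **Section 4, allocation.** State that children are randomised in permuted blocks of 3 within two age strata, 6-9 and 10-13 years, and whether one pair of lists serves both centres. A pair for each centre would make four strata and more incomplete blocks. Two age strata reduce the chance of a gap above 1 year to about 5-7%; they do not remove it.

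**Section 4.2, analysis.** Adjust the between-group comparison for age in a form that acts on change: either an age-by-time term in the repeated-measures model, or ANCOVA of follow-up on baseline and age. A main effect of age stratum alone would leave the group-by-time test as it was.

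**Cost.** A second allocation list and a small model change, with no extra children. If the strata do not fill in multiples of 3, one ends one child and the other two children into a block. The groups then have 14 each (42 in all) plus three children shared between them, so sizes can be 14-16 instead of exactly 15. The adjustment takes few degrees of freedom: one for age in the ANCOVA, or one for age and two for age-by-time over three assessments.

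### Two centres, but neither the described allocation nor the stated ANOVA accounts for centre: a modest, cheaply avoidable loss of balance and precision at 15 per group

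*Protocol*

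**What the plan says.** Protocol section 4 gives the whole allocation description in one sentence: "The 45-person study group will be randomized to 3 groups of 15 persons each". It mentions no stratification, blocking or list per centre. Section 4.1 repeats the total of 45.

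Section 5 places the study in one "special education and rehabilitation center and" a second of the same kind. The number of children expected from each is not given.

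Section 4.2 fixes the comparison: "The difference between the groups will be tested by two-factor variance analysis". It then explains that this design "is an independent variable with two or more groups and associated or repeated measurements". So the two factors are training group and assessment time. Section 4 sets three assessment times: before the study, at its end, and 3 months after its end. Centre is neither an allocation factor nor a model factor.

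**The concern.** Ordinary education is part of every arm: the first group receives only that, and section 3 asks whether adding physiotherapy to it helps. If the two centres differ in schooling over the 12 weeks and the 3-month follow-up, children could change at different rates according to centre, whatever their group. If one group then happens to hold more children from the faster-changing centre, part of that difference appears in the group contrast. Centre variation that is not modelled also stays in the error term.

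Only a centre difference in **change** matters for the group-by-time test, which section 4.2 describes as its purpose. A constant difference in level between centres cancels there.

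At stake is the size of the estimated contrast in the trial as it is actually allocated, and some power in a study that has little to spare. In a two-group t test, 15 per group gives 80% power only for a difference of about 1.06 SD.

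**Working it through.** **Inputs from the protocol.** 45 children, 3 groups of 15 (3 × 15 = 45, which agrees with section 4.1); two centres; factors group and time; significance level 0.05. No power, effect size or SD is given, so there is no sample-size calculation to reproduce.

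**Assumptions.** The centre split (10/35, 15/30 or 22/23), the centre difference in change γ (0 to 1.0 SD) and a 1.0 SD advantage for one group. None is in the protocol.

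**1. Chance imbalance if allocation ignores centre.** With K children from one centre, the probability that the three groups receive a, b and c of them (a + b + c = K) is C(15,a)·C(15,b)·C(15,c) / C(45,K). Summing over all cases with a gap of 4 or more:

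| Split | Two given groups differ by ≥ 4 | Largest gap among three groups ≥ 4 |
|---|---|---|
| 10/35 | 0.13 | 0.28 |
| 15/30 | 0.18 | 0.36 |
| 22/23 | 0.21 | 0.42 |

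The first column is the one that belongs with a named contrast, such as group 3 against group 2.

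**2. Shift in that contrast.** A 4-child gap shifts it by γ × 4/15 = 0.27γ:
- γ = 0.3 SD: 0.08 SD
- γ = 0.5 SD: 0.13 SD
- γ = 0.8 SD: 0.21 SD

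The standard error of a two-group contrast with 15 per group is √(2/15) = 0.37 SD. The shift is therefore about 0.2 to 0.6 of a standard error (0.08/0.37 to 0.21/0.37).

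**3. Type I error.** In simulated trials (one-way ANOVA on a change score, 22/23 split, γ of 0, 0.5 and 1.0 SD), the overall rate was 0.048 to 0.056 without centre and 0.051 to 0.055 with it. Among allocations where the largest gap was 5 or more (about 22% of them), the rate without centre was about 0.07 at γ = 0.5 and 0.09 at γ = 1.0.

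**4. Power for one group better by 1.0 SD in change.** Without centre, the error variance grows by γ² × (22 × 23)/45² = 0.25γ². The noncentrality is 15 × (2/3) × 1² / (1 + 0.25γ²) = 10/(1 + 0.25γ²), on 2 and 42 degrees of freedom. With allocation balanced by centre and centre in the model, it stays at 10, on 2 and 41.

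| γ (SD) | Noncentrality without centre | Power without centre | Power balanced, with centre |
|---|---|---|---|
| 0 | 10.0 | 0.79 | 0.78 |
| 0.5 | 9.4 | 0.76 | 0.78 |
| 0.8 | 8.6 | 0.72 | 0.78 |
| 1.0 | 8.0 | 0.68 | 0.78 |

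Simulation agrees to within about 0.01: 0.75 to 0.77, 0.73, and 0.68 to 0.69 without centre at γ = 0.5, 0.8 and 1.0.

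**The case against.** The strongest case against the point has five parts.

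- **The protocol is silent; it does not state unstratified allocation.** This is correct. The sentence in section 4 treats the 45 children as one group, but it would be compatible with lists kept by centre. A reader might infer that a single pooled list is specified; the text does not go that far.
- **Randomisation already accounts for chance imbalance.** This stands. A reader might infer that centre imbalance makes false positives more likely than 5%. Over all allocations it does not, and the conditional excess is modest even with large assumed centre effects.
- **Nothing shows that the centres differ in change.** This also stands. The protocol reports no difference in schooling, trainers or testers, and for the intelligence tests it refers to a single expert psychologist. The centre effect is an assumption throughout.
- **A centre term could stand in a statistical analysis plan that is not shown.** This is partly right. But section 4.2 does not leave the model open: it names a two-factor analysis and defines both factors. Allocation must be settled before the first child is randomised, and no later plan can change it.
- **A centre main effect would not help the group-by-time test, and small fixed blocks can be guessed.** Both are right. The remedy therefore needs centre-by-time, and blocks that are concealed and vary in size.

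**Conclusion.** The point holds as a modest design weakness: two centres, no described balancing by centre, and no centre term in the stated model. It does not invalidate the trial or bias it systematically.

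For a named contrast, a gap of 4 or more children arises in about 13% to 21% of unstratified allocations and moves the estimate by 0.27 of the centre difference in change. The loss of power is about 0.05 to 0.06 at a 0.8 SD centre difference and about 0.10 at 1.0 SD, with little loss at 0.5 SD or below. If the centres do not differ, nothing material is lost by including centre.

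The 42% figure for the largest gap among three groups should not be paired with the shift in a single contrast; for that, the corresponding figure is 21%.

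All of this rests on assumed centre sizes, assumed centre effects and an assumed 1 SD training effect, and on reading the allocation sentence as unstratified. The allocation half is the firmer part.

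**What to change.** In section 4, state that randomisation is done separately within each centre, using concealed permuted blocks of varying size, with about 15 per group overall. For illustration, if the split were 22/23, allocations of 7/7/8 and 8/8/7 would give 15 per group.

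In section 4.2, add centre and centre-by-time to the repeated-measures ANOVA; equivalently, include centre as a factor in an analysis of change. Centre as a main effect alone is not enough, because it adjusts the average level and not the group-by-time test.

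The cost is a second allocation list, a sentence in each section, one between-subject degree of freedom, and the centre-by-time terms (two degrees of freedom with three assessments). No extra children are needed.

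The limit should be stated too: if the centres deliver the training differently, that is a treatment-by-centre interaction, and neither stratified allocation nor these centre terms removes it.

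### Does the thin description of group 2's balance training undermine the comparison with dual-task training?

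*Protocol*

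**What the plan says.** Section 4 randomises 45 children to three groups of 15. Group 1 has education only. Group 3 has dual-task balance training. Of group 2 the protocol says: "The second group will be the control group and will be taken to the balance training in addition to normal education".

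After the arms have been introduced, section 4 gives a schedule without naming an arm: "The studies were planned to be 2 times a week for 12 weeks".

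The one detailed programme stands at the end of section 4, under the dual-task heading. It has a 10-minute warm-up, half of it on a treadmill, and then the main part: "The 20-minute Dual Task balance training program is planned to be composed of two sections of 10 minutes". The sections are described in turn: "In the first 10 min section, the individual will exercise with the multi-task mode of CogniBoard on the balance ball" and "Stroop study will be performed on the balance ball in the second 10 minutes of the exercise".

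The title names the question as "Effect of dual task balance training on cognitive functions in people with mental retarded". Section 3 words the purpose more broadly: whether adding physiotherapy to the education of these children benefits mental performance. Section 4.2 gives the analysis: "The difference between the groups will be tested by two-factor variance analysis". It singles out no pair of groups.

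**The concern.** In a three-arm design of this kind, the middle arm shows which part of the treatment does the work. Group 3 against group 1 mixes exercise, contact time and the cognitive task. Only group 3 against group 2 could isolate the cognitive task, and only if the two groups match in balance exercise and session time.

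The protocol does not state such a match. It gives group 2 neither exercises nor minutes, and it does not say that group 2 follows group 3's programme with the cognitive task removed. A reader could therefore fear that a difference between the trained groups comes from different exercises or unequal time and is then reported as the effect of the dual task. Section 5 names two centres, so one might also worry that each fills the gap in its own way. What an arm receives is protocol content; an analysis plan would not normally supply it.

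**Working it through.** The protocol states no figure for group 2's training time, so there is none to reproduce. The check sets the statements about each trained group side by side and does the little arithmetic they allow.

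**Inputs, all from section 4**

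| Item | Group 2 | Group 3 |
|---|---|---|
| Frequency and duration | 2 per week, 12 weeks (general statement, no arm named) | 2 per week, 12 weeks (general statement, repeated under the dual-task heading) |
| Warm-up | Not stated; may be shared | 10 min |
| Main part | Not stated | 2 sections of 10 min |
| Content of main part | Balance training, no exercises listed | CogniBoard on the balance ball, then Stroop on the balance ball |

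**Arithmetic**

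- Sessions = 2 x 12 = 24.
- Group 3, total = 24 x (10 + 20) = 720 min = 12 h.
- Group 3, dual-task part = 24 x 20 = 480 min = 8 h.
- Group 3, warm-up = 24 x 10 = 240 min = 4 h.
- Group 2, sessions = 24 on the natural reading of the general schedule. Total minutes = 24 x (minutes per session), and the second factor is not given, so the total cannot be computed.

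The group 3 total takes the 10-minute warm-up as additional to the 20-minute main part, which is how the section reads.

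**Could group 2's programme be read from the dual-task section?** Only in part. The heading is plural, its opening sentences speak of balance training generally, and the warm-up sentence breaks off. Schedule and warm-up may therefore be meant for both trained groups. The main part cannot be borrowed in this way, because both of its sections include a cognitive task.

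**Does any statement conflict with another?** No. The sentence on group 2, the general schedule and the dual-task description can all hold together. They are consistent with matched groups and with unmatched groups.

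**What does the missing detail affect?**

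- *The test.* The groups are formed by randomisation, so the planned analysis compares the programmes as assigned, whatever group 2's sessions contain. The missing description alters neither the calculation nor the significance level.
- *The section 3 purpose.* Physiotherapy added to education, against education alone, is a comparison with group 1. It does not require groups 2 and 3 to match, although group 2 against group 1 still needs a described programme to be understood.
- *The title's question.* Calling a difference between groups 3 and 2 the effect of the dual task does require a match. This is a matter of interpretation, and it depends on what was delivered.

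**The case for a change.** The best case for a change is that the protocol itself calls group 2 the control and puts dual-task training in its title, so a reader will expect the contrast between the trained groups to carry the conclusion. The gap is not explained by removed text: the removed pages lie among the contact details and after the applicant heading, not in section 4. Even the generous reading, with schedule and warm-up shared, leaves group 2's balance exercises and their length unstated. One paragraph would close the gap without touching arms, numbers, visits or analysis.

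Much of this stands. The description is missing, and a full protocol would contain it. The step from there to a flaw in the plan does not stand. The text does not show the trained groups to be unmatched; it leaves the matter unstated. The two-centre worry is conjecture, since section 5 only names the centres and nothing suggests different local programmes. Section 4.2 names no contrast between groups 3 and 2 and makes no claim to isolate the cognitive component. The narrower wording that one would ask for, a difference between two programmes, is needed only if the groups prove unmatched.

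**Conclusion.** No change to the plan follows. This is a gap in description that those running the trial must fill in order to deliver group 2's sessions at all. No stated rule gives a wrong result, and the planned comparison remains a valid randomised one.

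The size of any effect cannot be given. Group 3 has 12 h of described training, 8 h of it dual-task; group 2 has 24 sessions of unstated length and content. Any figure for bias would be invented.

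The conclusion rests on two readings: that the general schedule covers both trained groups, and that the section 3 purpose stands alongside the title. If the title's question were taken as the sole aim, the missing description would matter more, but still for the wording of the conclusion and not for the analysis. Ordinary reporting of what each arm received will show whether a difference between groups 3 and 2 can be credited to the cognitive task or only to the programme as a whole.

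### Is CogniBoard, on which only the dual-task group is described as training, also an outcome measure that would reward practice on the device?

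*Protocol*

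**What the plan says.** Section 4 (Materials and Methods) describes its tools one after another: MOXO, WISC-R, BOT-2, CogniBoard, Functional Reach and the Pediatric Balance Scale. The CogniBoard entry says the device "provides multiple exercises, and develops and measures cognitive and motor performance in healthy individuals and athletes". It goes on to the panel of lighted buttons and the cues given during exercise, and ends "Thus, tactile, visual, proprioceptive and auditory feedback is provided".

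The paragraph on the dual-task programme, which follows the last of these entries, gives the device its use in the trial: "In the first 10 min section, the individual will exercise with the multi-task mode of CogniBoard on the balance ball". On what this is for, it says "This mode aims at neurocognitive procedures such as attention, short-term memory, hand-eye coordination, focusing and perception". On frequency it says "A progressive balance training program will be held twice a week for 12 weeks". A Stroop exercise fills the second 10 minutes.

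The groups are set out earlier in Section 4. One has schooling alone: "The first group will not be subjected to any application except education". Another adds balance work, with no mention of CogniBoard: "The second group will be the control group and will be taken to the balance training in addition to normal education". The last receives the programme that uses the device; its training is described separately, as quoted above.

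Assessments take place before training, at its end and three months later, and are compared within and between groups. The protocol does not list which tools make up those assessments.

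**The concern.** Every other entry in that run of descriptions is an assessment, and this one says that its device measures performance. The intervention has its own paragraph further on, where one would expect to find equipment used only for training. A reader could therefore take CogniBoard to be one of the instruments applied at the three assessment times.

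On that reading the design has a real weakness. One group would be tested on the device it had trained on for 12 weeks, against groups with no described training on it. Randomisation does not help, because the practice comes after allocation and belongs to one arm. The group-by-time analysis of variance in Section 4.2 could not tell familiarity with the lights and buttons from a gain in attention or memory. Section 3 asks whether adding physiotherapy helps mental performance, so a gain on the trained device might be reported as a cognitive benefit without any transfer to other tasks.

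**Working it through.** The protocol gives no effect size, standard deviation or power for this point, so there is no stated figure to reproduce. The check is one sum and a reading of the text.

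**Planned exposure to the device**

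Inputs, all from Section 4: 2 sessions a week, 12 weeks, 10 minutes of CogniBoard per session.

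- Sessions: 2 × 12 = 24.
- Dual-task group: 24 × 10 = 240 minutes.
- Education-only group: 0 minutes, since it receives education alone.
- Balance-training group: none stated. The content of its training is not described, so zero is an inference.

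The Stroop exercise also comes to 24 × 10 = 240 minutes in the dual-task group.

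**Is a CogniBoard score an outcome?**

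1. *The measuring claim.* The sentence is about healthy individuals and athletes. The trial enrols children aged 6 to 13 with IQ 50 to 79. It states what the product can do in general, not what this trial will measure.
2. *The rest of the entry.* It covers hardware, exercise and feedback. It names no score, scale, test mode or testing procedure.
3. *The name.* Each neighbouring entry is called a test or a scale. CogniBoard is called a device.
4. *The assessment schedule.* It gives three time points and does not name CogniBoard.
5. *Section 4.2 (Statistics).* It names the analysis and a significance level of 0.05. It names no CogniBoard endpoint, and it does not say that one significant result on any measure would establish benefit.
6. *Stroop.* It appears only as an exercise in the training paragraph, and nothing presents it as a measure.

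The only use of CogniBoard that the protocol states for this trial is therefore training.

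**What if a score were compared anyway?**

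The dual-task group would have up to 240 minutes more practice by the end of training. The practice bias would run in its favour, but its size cannot be derived, because the protocol gives no link between minutes and score. Nor would the score necessarily show practice alone. It could reflect both practice and better cognition, and the design could not divide the two.

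**What remains for the cognitive question?**

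MOXO (attention) and WISC-R (intelligence) are both described in Section 4, and neither is described as training content for any group. A conclusion resting on them does not share this device-specific problem. The intelligence-related assessments are assigned to an expert psychologist.

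**The case for a change.** The strongest argument for a change is position and cost. CogniBoard stands between BOT-2 and Functional Reach, its entry gives it both a training and a measuring role, and nothing excludes it from the unlisted assessments. The trained mode is aimed at attention and short-term memory, which are close to what the trial wants to show, and no primary outcome is named to hold the conclusion to another test. One sentence would settle the device's role, with no added tests or visits.

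Much of this is correct. The role is left unstated, and a between-group comparison of a CogniBoard score would be confounded with practice. That the untrained groups have no device time is certain for the education-only group and a reasonable inference for the balance-training group.

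The step from there to an error in the plan does not stand. Position in a run of descriptions is weak evidence of an outcome, since introducing equipment before the paragraph that uses it is just as natural. The proposed sentence would disclaim an outcome that the protocol never claims. For Stroop even the argument from position is absent. If the device stores scores, an analyst would ordinarily treat them as a record of training progress, and a list of outcomes can properly be left to a statistical analysis plan, which is not shown here.

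**Conclusion.** No change follows. This is a gap in description that analysts can fill sensibly. The protocol leaves the role of CogniBoard less clear than it might, but the only use it states is training in the dual-task arm, and it fixes no comparison that practice would bias.

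The one figure is 240 minutes of planned device time in the dual-task group, against none in the education-only group and none stated in the balance-training group. It describes exposure and does not size a bias.

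The conclusion rests on two assumptions: that the measuring claim is general product text, as its reference to healthy individuals and athletes suggests, and that the cognitive conclusion will rest on MOXO and WISC-R. If a CogniBoard score were instead reported as between-group evidence of better cognition, the practice objection would apply in full to that result.
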